### Regulatory Statement

This study will be performed in compliance with the protocol and in accordance with Good Clinical Practice (International Conference on Harmonisation [ICH], Guidance E6, 1996), principles of human subject protection, and applicable country-specific regulatory requirements.

## SYNOPSIS

Protocol Title:	A Phase 2, Multi-Center, Randomized, Double-Masked, Saline-Controlled Study to Evaluate the Effect of Perfluorohexyloctane (NOV03) at Two Different Dosing Regimens on Signs and Symptoms of Dry Eye Disease
Protocol Number:	NVU-002
Study Drug:	NOV03 ( [REDACTED] Perfluorohexyloctane)
Control:	Saline solution: 0.9% sodium chloride solution
Study Phase:	2
Study Objective:	
The primary objective for this study is to evaluate the efficacy, safety, and tolerability of perfluorohexyloctane (NOV03) at two different dosing regimens compared to saline solution in subjects with Dry Eye Disease.
 
[REDACTED]
 
[REDACTED]
 
[REDACTED]
 
[REDACTED]
 
[REDACTED]

Overall Study Design	
Structure:	Multi-center, randomized, double-masked, saline-controlled
Duration:	An individual subject’s participation is estimated to be approximately 10 weeks.
Dosage/Dose Regimen:	
Subjects eligible to be randomized will receive one of the following treatments to be administered bilaterally from Visit 1 to Visit 4.
 

1) NOV03 ( [REDACTED] Perfluorohexyloctane) 4 times daily (QID)

2) NOV03 ( [REDACTED] Perfluorohexyloctane) 2 times daily (BID)

3) Saline solution (0.9% sodium chloride solution) QID

4) Saline Solution (0.9% sodium chloride solution), BID

	
[REDACTED] [REDACTED]
 
■ [REDACTED] [REDACTED] [REDACTED] [REDACTED]
 
h. Have an ocular or periocular malignancy.
 
■ [REDACTED] [REDACTED]
 
j. Have a history of herpetic keratitis.
 
k. Have active ocular allergies or ocular allergies that are expected to be active during the study period.
 
l. Be diagnosed with an ongoing ocular or systemic infection (bacterial, viral, or fungal), including fever and current treatment with antibiotics.
 
m. Have worn contact lenses within 1 month of Visit 0 or anticipate using contact lenses during the study.
 
■ [REDACTED] [REDACTED] [REDACTED] [REDACTED]
 
■ [REDACTED] [REDACTED] [REDACTED] [REDACTED]
 
p. Be a woman who is pregnant, nursing or planning a pregnancy.
 
q. Be unwilling to submit to a blood pregnancy test at Visit 0 and Visit 4 (or early termination visit) if of childbearing potential. Non-childbearing potential is defined as a woman who is permanently sterilized (e.g. has had a hysterectomy or bilateral tubal ligation or

--	--

	
bilateral oophorectomy), or is post-menopausal (without menses for 12 consecutive months).
 
r. Be a woman of childbearing potential who is not using an acceptable means of birth control; acceptable methods of contraception include: hormonal – oral, implantable, injectable, or transdermal contraceptives; mechanical – spermicide in conjunction with a barrier such as a diaphragm or condom; intrauterine device (IUD); or surgical sterilization of partner. For non-sexually active females, abstinence may be regarded as an adequate method of birth control; however, if the subject becomes sexually active during the study, she must agree to use adequate birth control as defined above for the remainder of the study.
 
s. Have an uncontrolled systemic disease.
 
t. Have a known allergy and/or sensitivity to the study drug or saline components.
 
■ [REDACTED] [REDACTED] [REDACTED] [REDACTED]
 
■ [REDACTED] [REDACTED] [REDACTED]
 
w. Have used any topical steroids treatments, topical cyclosporine, lifitegrast, serum tears or topical anti-glaucoma medication within 60 days prior to Visit 0.
 
■ [REDACTED] [REDACTED] [REDACTED] [REDACTED] [REDACTED] [REDACTED] [REDACTED] [REDACTED]
 
y. Have corrected visual acuity greater than or equal to logarithm of the minimum angle of resolution (logMAR), [REDACTED] as assessed by Early Treatment of Diabetic Retinopathy Study

--	--

	
[REDACTED]

Safety Endpoints:	

• Visual Acuity.

• Slit-Lamp Biomicroscopy.

• Intraocular Pressure.

• Dilated Fundoscopy.

• Hematology/Chemistry parameters.

• Systemic and ocular adverse events.

• Symptoms directly related to the instillation or use of the investigational medication based on questionnaire/visual analogue scale.

Other:	

• Pharmacokinetics of perfluorohexyloctane (blood levels for perfluorohexyloctane at predefined time points and PK parameters as appropriate).

General Statistical Methods and Types of Analyses
 
Sample Size At least 300 subjects (100 each for the two active arms, and 50 each for the two saline solution arms) will be randomly assigned to study treatment such that approximately 90 evaluable participants per active arm and 45 per saline solution arm complete the study, assuming a 10% dropout rate.
 
Primary Efficacy Analyses: The primary evaluation of efficacy of the active arms will be against a combined control arm (with BID and QID saline solution). Sensitivity analysis may be undertaken for dosing-regimen matching control (that is, QID active vs. QID saline solution). The primary analysis will be performed to compare the week 8 difference in the change from baseline in CFS between the active NOV03 groups and the saline solution groups. The comparison will be conducted using a repeated measures model with treatment, site, visit, and treatment by visit interaction fixed categorical factors, baseline as a continuous covariate, and using an unstructured covariance matrix. To establish evidence of efficacy in this proof of concept study, the hypothesis tests will be one-sided and performed at the 0.05 significance level.
 
[REDACTED]
 
[REDACTED]
 
[REDACTED]
 
[REDACTED]
	

### Safety Variables

Adverse events (AEs) will be coded using the MedDRA dictionary. Frequencies and percentages of subjects with treatment-emergent adverse events (TEAEs), serious TEAEs, and TEAEs causing premature discontinuation will be provided by treatment group. An AE is treatment emergent if it occurs or worsens after the patient signed Informed Consent Form (ICF). Furthermore, frequencies will be given of subjects with TEAEs by system organ class; by system organ class and preferred term; by system organ class, preferred term and maximal severity; by system organ class, preferred term and strongest relationship; and by system organ class, preferred term, maximal severity, and strongest relationship. Separate summaries will be performed for ocular and non-ocular AEs.

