### **3.5 Re-Screen Procedures**

If the patient does not qualify at Visit 0 or Visit 1, he or she may be re-screened after 14 days from the relevant visit provided that new informed consent to be signed, new screening number received via IWRS and all the assessments are repeated as per protocol requirements.

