#### 5.4.1 Dispensation Schedule

- Study drug will be provided to sites as subject kits containing 2 bottles of NOV03 or saline solution.
- At the end of Visit 1, qualified subjects will be randomized and the first dose of study drug will be administered in the study center. The subject will receive the first subject kit. Subjects will be instructed to only open one bottle at a time. They should be instructed not to discard the empty bottles but return them at their next visit. Subjects will record in their diary that their doses were taken.
- At Visit 2, used/unused study drug will be collected from subjects for drug accountability. The subject will be dispensed a new subject kit to continue daily dosing. Subjects will be instructed to only open one bottle at a time. They should be instructed not to discard the empty bottles but return them at their next visit. Subjects will record in their diary that their doses were taken.
- At Visit 3 used/unused study drug will be collected from subjects for drug accountability. Subjects will receive two subject kits. Subjects will be instructed to only open one bottle at a time. They should be instructed not to discard the empty bottles but return them at their next visit. Subjects will record in their diary that their doses were taken.
- At Visit 4 used/unused study drug will be collected from subjects for drug accountability.
- Subjects will be instructed to immediately contact the site if there is any problem with the study drug, e.g. kit/bottle(s) was damaged or lost or if the open bottle was dropped. In case the subject needs a replacement, a new kit is assigned to the subject.

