## 7 ADVERSE EVENTS

### 7.1 Adverse Event

An adverse event (AE) is defined as any untoward medical occurrence associated with the use of a drug in humans, whether or not the event is considered drug-related. An AE can therefore be any unfavorable and unintended sign (eg, an abnormal laboratory finding), symptom, or disease occurring after the subject signed Informed Consent Form (ICF) without any judgment about causality.

If there is a worsening of a medical condition that was present prior to the administration of the study drug, this should also be considered a new AE and reported. Any medical condition present prior to the administration of the study drug that remains unchanged or improved should not be recorded as an AE at subsequent visits.

Worsening of Dry Eye Disease will be considered an AE only if the dry eye status of the subject exceeds their previous experiences with the condition. This will be determined by the subject and the investigator.

A clinically significant visual acuity decrease (defined as an increase of 0.22 or greater in logMAR score) from baseline (Visit 0) will be considered an Adverse Event.

Study drug includes the investigational drug under evaluation and any comparator drug, placebo, or any other medications required by the protocol given during any stage of the study.

Documentation regarding the AE should be made as to the nature, date of onset, end date, severity, relationship to study drug, action(s) taken, seriousness, and outcome of any sign or symptom observed by the physician or reported by the subject upon indirect questioning.

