### 8.4 Statistical Analysis

#### 8.4.1 General Considerations

Quantitative variables will be summarized using number of subjects (n), mean, median, standard deviation, minimum and maximum. The qualitative variables will be summarized using counts and percentages.

All summaries will be presented by treatment group, with placebo presented both pooled as well as separately for QID and BID dosing. Summaries will be provided for demographics, baseline medical history, concurrent therapies, and subject disposition.

For the purpose of summarization, medical history, concurrent therapies, and AEs will be coded to MedDRA and WHO Drug dictionaries, as appropriate.

Baseline measures are defined as the last non-missing measure prior to the initiation of randomized study treatment.

All primary [REDACTED] will be one-sided at a significance level of 0.05.

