#### **Analysis of Adverse Events**

Adverse events will be coded using the MedDRA dictionary. Frequencies and percentages of subjects with treatment-emergent adverse events (TEAEs), serious TEAEs, and TEAEs causing premature discontinuation will be provided by treatment group. An AE is treatment emergent if it occurs or worsens after the first dose of study treatment. Furthermore, frequencies will be given of subjects with TEAEs by system organ class, by system organ class and preferred term, by system organ class, preferred term and maximal severity, by system organ class, preferred term and strongest relationship, and by system organ class,

preferred term, maximal severity, and strongest relationship. Separate summaries will be performed for ocular and non-ocular AEs.

The treatment groups will be compared in regard to safety endpoints descriptively. No inferential comparison will be conducted.

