### **Analysis of Laboratory Parameters**

Clinical laboratory parameters including hematology and serum chemistry will be summarized by treatment group and by visit. Baseline values, the values at each subsequent visit, and changes from baseline will be summarized for each of the quantitative laboratory assessments by treatment. Shift tables of chemistry and hematology, results will be used to summarize changes from baseline to study termination (or early termination). The number and percentage of chemistry and hematology values outside of normal ranges and/or with potential clinical importance will be summarized by visit and treatment.

Other safety endpoints including visual acuity, slit-lamp biomicroscopy, dilated funduscopy, safety laboratory, and intraocular pressure will be summarized by treatment group and visit using descriptive statistics. Changes or shifts from baseline will also be summarized where appropriate. For assessments performed by eye, study eye and fellow eye will be summarized separately. In addition, shifts from baseline to worst on-treatment value for ocular safety assessments will be summarized.

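### The synopsis starts treatment-emergent AEs at consent and Section 8.4.7 starts them at first dose, for the same by-arm safety tables

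*Combined protocol and SAP*

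**What the plan says.** The synopsis, under Safety Variables, states: "An AE is treatment emergent if it occurs or worsens after the patient signed Informed Consent Form (ICF". Section 8.4.7, under Analysis of Adverse Events, states: "An AE is treatment emergent if it occurs or worsens after the first dose of study treatment".

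The text around the two sentences is otherwise nearly the same. Both places call for TEAEs, serious TEAEs and TEAEs leading to discontinuation by treatment group. Both ask for the same breakdowns by system organ class, preferred term, maximal severity and strongest relationship, and for the same split into ocular and non-ocular events.

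On timing, Section 2.4 places consent at the screening visit, before any study procedure, and Table 1 puts that visit within 14 days before Visit 1. Section 5.4.1 places the first dose later: "At the end of Visit 1, qualified subjects will be randomized and the first dose of study drug will be administered". Section 7.1 defines an adverse event as any unfavourable sign, symptom or "disease occurring after the subject signed Informed Consent Form (ICF) without any judgment about causality". Section 6.4.1 lists an adverse event query at Visit 1 ahead of randomization and the in-office dose.

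**The concern.** The two starting points cannot coincide, so the two sentences define different tables. A programmer who follows the synopsis and one who follows Section 8.4.7 could report different TEAE counts from the same database, and no visible text says which rule governs.

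Under the synopsis rule, an event that began in screening would be counted as treatment emergent in a named arm although no treatment had been given. Safety and tolerability are part of the primary objective (Section 2.1.1), and Section 1.3 says the data will be used to plan phase 3. The absolute TEAE percentages should therefore mean one thing.

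**Working it through.** **1. Are the two sentences about the same tables?** Yes. The summaries requested around them match item by item, as set out above. Both are current text and neither is redacted.

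**2. Can a pre-dose event reach the data for a dosed subject?** Yes. Section 7.1 defines events from consent, and Section 6.4.1 queries them at Visit 1 before the dose. Section 7.1 also gives a concrete route: a rise of 0.22 or more in logMAR score from Visit 0 is an adverse event, and Section 6.4.1 lists visual acuity at Visit 1 ahead of randomization. If such a subject still qualifies and is dosed, the event is a TEAE under the synopsis and not under Section 8.4.7.

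Section 7.1 narrows this in one respect: "Any medical condition present prior to the administration of the study drug that remains unchanged or improved should not be recorded as an AE" at later visits. That limits repeat recording after dosing. It does not prevent a first record at Visit 1, before the dose.

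**3. How much of the synopsis window precedes dosing?**

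Inputs: screening period s of up to 14 days (Section 2.2, Table 1); first dose on Day 1 (Section 5.4); Visit 4 on Day 57 ± 2 (Section 2.4).

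Formula: pre-dose share = s / (s + T), where T is the time from first dose to Visit 4.

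- Elapsed days, T = 57 − 1 = 56: 14 / (14 + 56) = 14/70 = 20.0%.
- Calendar days of the stated treatment period, T = 57: 14 / (14 + 57) = 14/71 = 19.7%.
- Visit 4 at the edges of its window: Day 55 (T = 54) gives 14/68 = 20.6%; Day 59 (T = 58) gives 14/72 = 19.4%.
- Shorter screening, assumed to be 7 days, with T = 56: 7/63 = 11.1%.

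These are shares of time for a subject who completes to Visit 4. They become shares of background events only if the background rate is constant over screening and treatment, which is an assumption.

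**4. How many events would move?** This cannot be calculated. The documents give no background adverse event rate. On the subject-level scale of the tables, a percentage moves only when a dosed subject has a pre-dose event in a category and no later event in that category.

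**5. Is any test affected?** No. Section 8.4.7 states that safety comparisons are descriptive, and no efficacy analysis uses the TEAE definition.

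**The case against.** The strongest case on the other side is that this is a drafting slip in a synopsis. The detailed methods section already has the first-dose definition, and a statistician would probably program from it. The tables cover dosed subjects only (Section 8.1). Pre-dose events precede treatment, so they should add similar background to every arm, which tends to dilute differences between arms and not to favour one. All of that stands, and it limits the weight of the point. It does not remove the contradiction. Section 8.4.3 mentions a separate SAP, and Appendix 5 is listed as a summary of changes; whether either settles the matter cannot be judged from the text available.

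A reader might infer more than the documents support:

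- *That the synopsis rule also contradicts the baseline and shift rules.* Section 8.4.1 says "Baseline measures are defined as the last non-missing measure prior to the initiation of randomized study treatment", and Section 8.4.7 says "shifts from baseline to worst on-treatment value for ocular safety assessments will be summarized". These govern measurements, not the onset of adverse events. Nor is everything anchored at first dose: the visual acuity criterion in Section 7.1 takes Visit 0 as its baseline.
- *That the synopsis window is undefined, and much longer, for re-screened subjects.* Section 3.5 allows re-screening "provided that new informed consent to be signed, new screening number received via IWRS". But Section 9.6 says data are not entered for screen failures, so on the natural reading events from a failed first attempt would not reach the tables.
- *That Section 7.1 supports the synopsis.* It sets what is collected as an adverse event. Collecting from consent is compatible with counting as treatment emergent only from first dose.
- *That the SAE text is part of the same fault.* Section 7.3.1 starts SAE reporting at the start of study product, Section 6.4.2 has SAEs monitored throughout the study, and Section 7.1 defines events from consent. Monitoring and reporting windows can differ, so this is a separate and minor matter of clarity.

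**Conclusion.** The point holds as a direct contradiction between the synopsis and Section 8.4.7 on when an adverse event becomes treatment emergent. Up to about 20% of the synopsis window precedes any dose, assuming a full 14-day screening and completion to Visit 4; with shorter screening the share is smaller. Absolute TEAE percentages could be higher under the synopsis rule, by an amount the documents do not allow one to calculate.

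The documents do not support a claim that one arm is favoured, that a safety comparison is biased in a known direction between active and saline, or that any efficacy or inferential result changes. The correction should be made because the rule as written in the synopsis would label pre-treatment events as treatment emergent, and because it is cheap.

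**What to change.** In the synopsis, replace the TEAE sentence with the one in Section 8.4.7: "An AE is treatment emergent if it occurs or worsens after the first dose of study treatment". Do this before database lock and unmasking, so that the choice cannot appear to depend on the data. Adverse events with onset between consent and first dose may be listed separately for dosed subjects; this is useful but not needed to resolve the contradiction.

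As a separate minor item, reconcile Sections 6.4.2, 7.1 and 7.3.1 so that one SAE reporting window is stated.

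Cost: one synopsis sentence, one clarifying sentence on SAE reporting and, if wanted, one listing. Design, sample size and efficacy analysis are unchanged.

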### Pharmacokinetics

Whole blood for perfluorohexyloctane blood concentration measurements will be drawn from a minimum of 66 subjects at least at one investigational site with the goal of having samples from 20 subjects per treatment arm. Blood concentrations of perfluorohexyloctane will be summarized descriptively. If possible, the following PK parameters will be estimated:  $AUC_{0-\tau}$ ,  $C_{max}$ ,  $t_{max}$  and summarized descriptively.

## LIST OF ABBREVIATIONS

AE	adverse event
AUC 0-last	Area under the blood concentration time curve from time 0 to time of last measureable concentration
BAC	benzalkonium chloride
BCVA	best-corrected visual acuity
BID	Two times daily
CFR	Code of Federal Regulations
C max	Maximum blood concentration
CRF	case report form
CV	Coefficient of variation
DED	Dry Eye Disease
DEWS	Dry Eye Workshop
eCRF	electronic case report form
ETDRS	Early Treatment of Diabetic Retinopathy Study
FDA	Food and Drug Administration
GCP	Good Clinical Practice
HIPAA	Health Information Portability and Accountability Act
ICF	informed consent form
ICH	International Conference on Harmonization
IEC	Independent Ethics Committee
IND	investigational new drug
IOP	intraocular pressure
IRB	institutional/independent review board
IUD	Intra-uterine device
IWRS	interactive web response system
logMAR	logarithm of the minimum angle of resolution
LLT	lipid layer thickness
LS mean	Least square mean
MCH	Mean cell hemoglobin
MCHC	Mean cell hemoglobin concentration
MCV	Mean cell volume
MedDRA	Medical Dictionary for Regulatory Activities
MGD	meibomian gland dysfunction
mITT	modified intent-to-treat
NEI	National Eye Institute
NOV3	█████ perfluorohexyloctane
OD	right eye
OS	left eye
OSDI ®	ocular surface disease index
PP	per protocol
QID	four times a day
SAE	serious adverse event
SAP	Statistical Analysis Plan

TEAEs	Treatment-emergent adverse events
TFBUT	tear film break-up time
TFT	tear film thickness
$t_{\max}$	time to $C_{\max}$
VA	visual acuity
VAS	visual analog scale

# 1 INTRODUCTION

## 1.1 Dry Eye Disease (DED)

Dry Eye Disease (DED) is defined by the International Dry Eye Workshop (DEWS) as a multifactorial disease of the ocular surface characterized by a loss of homeostasis of the tear film, and accompanied by ocular symptoms, in which tear film instability and hyperosmolarity, ocular surface inflammation and damage, and neurosensory abnormalities play etiological roles. Estimates of the prevalence of dry eye vary considerably, depending on the criteria used to define the disease, but in the United States (US), it has been estimated that as many as 3.2 million women and 1.7 million men over the age of 50 have DED, with a projected 40% increase in the number of patients affected by 2030. With the aging population in the US and other countries of the developed world, and with increasing computer use, DED is expected to continue to become more prevalent and finding a treatment is becoming more important.

